Hence, we will also look for any differences in pain, nausea and vomiting over the first 24 hrs after the surgery, along with chances of readmission or ER visits within the same period, post discharge. At 3 months, we will look for the incidence of persisting pain after surgery.

Hypothesis

In patients who undergo ambulatory surgical procedures causing at least moderate pain, hydromorphone (HM) increases the proportion of patients who would demonstrate 'satisfactory analgesia [$=<4/10$ NAS] with minimal or no postoperative nausea-vomiting (PONV) [$<2/5$ VDS] as compared to morphine (M), when both are administered intravenously, in equianalgesic doses, and are compared at 2 hours after surgery in PACU.

2. Specific Objectives

The primary objective of this study is to compare the proportion of patients with SAME (satisfactory analgesia and minimal emesis) after AS, when using M compared with HM, during the immediate postoperative hospital stay.

Secondary objectives include:

1. Total dose of analgesic used in PACU, in morphine equivalents,
2. Time to discharge or readiness to discharge from the DSU,
3. Proportion of pain, and its comparison after discharge, within 24 hours,
4. Proportion of nausea, and its comparison after discharge, within 24 hours,
5. Proportion of vomiting, and its comparison after discharge, within 24 hours,
6. Incidence of CPSP at 3 months after discharge

The tertiary objectives include:

1. Proportion of patients with severe itching,

Protocol Version Date: Version 5 / June 23, 2015

Most Effective Opioid Analgesia in Ambulatory Surgeries: a randomized control, investigator blinded, parallel group with superiority design study of Morphine versus Hydromorphone

[name], Principal Investigator SJHH

[name], Principal Investigator HHS

2. Proportion of patients with significant sedation,
3. Proportion of patients with significant respiratory depression,
4. Patient satisfaction score at the time of discharge,
5. Time to discharge or readiness to discharge from the PACU,
6. Use of ketorolac as a rescue medication,

METHODS

The study is designed as a multisite, 2 arm, parallel, superiority design with randomization of patients and blinding of patients, health care providers (physicians and nurses) and research personnel (research coordinator and data analyst). Patients will be stratified based on site and laparoscopic/open surgeries. Intention to treat approach will be used for design and analysis.

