At the end of 2 hours or after satisfactory completion of primary endpoints, patients shall be transferred to DSU. At the DSU, in both groups, patients shall be given oral Oxycocet (combination of oxycodone and paracetamol) or Tylenol 3 (combination of codeine and paracetamol), as a PRN medication, if necessitated by the patient's pain. Nurses shall note down the occurrence of any pain and nausea necessitating treatment in the patient's CRF. Readiness to discharge home is noted down for each patient. The RA shall collect the CRFs from PACU and DSU and deposit safely in a locked filing cabinet.

Planned Outcomes: Our combined primary outcome will be proportion of patients with SAME, as compared between the 2 groups. Analgesia will be based on NAS 0-10 (appendix 3), and PONV will be based on VDS 0-5 (appendix 3). These observations will be made at the end of 2 hrs or before (corresponding to the time of discharge from PACU), by the PACU nurse, in the specified CRF. All the other outcomes to be recorded within the hospital, along with the time of their measurement and proposed analysis method are noted in table 1.

Sample Size Calculation: It was calculated based on the primary, binary outcome of proportion of patients with SAME, which will be compared using a chi-square test. According to literature,

Most Effective Opioid Analgesia in Ambulatory Surgeries: a randomized control, investigator blinded, parallel group with superiority design study of Morphine versus Hydromorphone
 [name], Principal Investigator SJHH
 [name], Principal Investigator HHS

approximately 30%-40% of patients are provided with inadequate analgesia after their AS,^(25, 26) with a similar number also known to suffer from PONV after AS.^(3, 24) Our chart reviews suggests that approximately 20% of patients suffer from inadequate analgesia with PONV using morphine. For a 2-sided test, with an alpha of 0.05 and a power of 90%, and with an estimated effect size of 10% (p1= 80% and p2= 90%), a sample size of 266 per group was calculated. However, for recruitment we shall have a target of 275 per group, for a total of 550 patients (rounding off). For the primary outcome analysis, we expect minimal loss through attrition as the study involves a follow up of few hours. The expected recruitment is approximately 20 cases per month at each of the 3 sites. We expect the trial to run for 10-12 months.

Table 1: Study Outcomes, and their Measurement and Analysis

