OUTCOME MEASURE	TYPE	MEASUREMENT	TIME OF MEASUREMENT	ANALYSIS METHOD
Primary outcome Satisfactory Analgesia with minimal PONV	Binary	NAS=<4/10 VDS<2/5	At 2hrs or at the time of discharge from PACU	Chi-square
Severe Itching	Binary	VAS>5/10	At 2hrs or at the time of discharge from PACU	Chi-square or Fisher's test (as appropriate)
Severe Sedation	Binary	Ramsey Score >3/6	At 2hrs or at the time of discharge from PACU	Chi-Square or Fisher's test (as appropriate)
Severe Respiratory Depression	Count	All cases needing treatment as counts	At 2hrs or at the time of discharge from PACU	Chi-square or Fisher's test (as appropriate)
Use of Ketorolac	Continuous	Total dose used per patients as a rescue therapy	At 2hrs or at the time of discharge from PACU	T test
Mean dose of Analgesic Used	Continuous	Dose of Analgesic used per patient in EMU	At the time of hospital discharge	T test

Most Effective Opioid Analgesia in Ambulatory Surgeries: a randomized control, investigator blinded, parallel group with superiority design study of Morphine versus Hydromorphone
 [name], Principal Investigator SJHH
 [name], Principal Investigator HHS

Patient Satisfaction-Mean score (0-10)	Continuous	Mean Score calculated between 0 to 5 scale	At the time of hospital discharge	T test
Time to discharge from PACU	Continuous	Mean time in hrs	At 2hrs or at the time of discharge from PACU	T test
Time to discharge from the hospital	Continuous	Mean time in hrs	At the time of hospital discharge	T test

Outcomes at Post-operative Day 1:

Patients will be approached by 1-2 phone calls shall be done during the next day; if unanswered, a repeat call will be made on the subsequent day (2nd day after discharge); for responders, the following questions will be asked.

1. What was your average pain score over the last 24 hrs, in 0-10 NAS scale, after you were discharged home?
2. After discharge, did you have nausea-severe enough to require medications at home?
3. After discharge, did you have vomiting-severe enough to require medications at home?
4. After discharged home, did you require a visit to ER, or readmission?

Outcomes at 3 months:

Patients will be contacted by a mailed package at 3 months after surgery to collect the following outcomes.

1	Do you have Persistent Pain (which started with or after surgery), at or near the surgical area?	Yes or No
2	Intensity of Pain	NAS: 0-10
3	Brief Pain Inventory-Interference Items 7 Items: each item scored between 0-10	

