The potential impact of the study could change the routine practice for anesthesiologists and other care providers. By choosing a better medication, physicians can be confident of their choice based on clear evidence, instead of a trial and error method in PACU management which usually leads to increased time with inferior results. The perceived advantages include better analgesia, less side effects, early discharge, reduced use of medications, less overall cost, and better patient satisfaction. These are truly reflective of what are proposed to be the most ideal outcomes for AS setting.⁽²⁾ These results could facilitate early discharge will require lesser costs due to savings on manpower. The study will also provide an estimate of incidence of pain, nausea and vomiting after discharge, within the first 24 hrs after surgery. The burden of such a problem will help to organize better health service provision in future, for patients of day surgeries. The study will also give us an indication of incidence of persistent postoperative pain; and also whether better control of their acute pain makes an impact on the incidence and severity of persistent pain at 3 months.

Most Effective Opioid Analgesia in Ambulatory Surgeries: a randomized control, investigator blinded, parallel group with superiority design study of Morphine versus Hydromorphone
[name], Principal Investigator SJHH
[name], Principal Investigator HHS

REFERENCES

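### Post-discharge nausea and vomiting are recorded only when they required medication, so the trial yields a lower bound on the incidence that its objectives and significance section promise

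*Combined protocol and SAP*

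**What the plan says.** Under Specific Objectives, secondary objective 4 is "Proportion of nausea, and its comparison after discharge, within 24 hours". Objective 5 is the same for vomiting. Neither names a threshold of severity or treatment. The Study Significance section adds: "The study will also provide an estimate of incidence of pain, nausea and vomiting after discharge", and says that knowing this burden will help to organize services for day-surgery patients.

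The data come from the telephone call described under Outcomes at Post-operative Day 1 and repeated in Appendix 1. The nausea item is "After discharge, did you have nausea-severe enough to require medications at home". The vomiting item has the same condition. Pain on the same call is an average score from 0 to 10 with no condition attached. The graded PONV scale in Appendix 3 is specified for the PACU assessment, not for the call.

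The sample size section concerns the primary outcome only. It states no rate, effect or power for post-discharge nausea or vomiting.

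**The concern.** The objectives and the instrument define different quantities. A patient who was nauseated at home, or who vomited, but judged that no medication was needed answers no and is counted with the symptom-free. What is estimated is the proportion with medication-requiring symptoms, although it would be reported under objectives that promise all nausea and all vomiting.

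The background section makes this matter. It argues that the symptom burden after ambulatory surgery should not be assumed to be small, and that such patients reach health services less easily than inpatients do. An item that leaves out symptoms not judged to need medication works against that rationale, and nothing else collected after discharge allows the missing part to be reconstructed.

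**Working it through.** **Objective against instrument.** The two sides, from the sections cited above:

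| | Promised | Collected |
|---|---|---|
| Nausea, 24 h after discharge | proportion and incidence, no threshold | yes/no, only if medication was required |
| Vomiting, 24 h after discharge | proportion and incidence, no threshold | yes/no, only if medication was required |
| Pain, 24 h after discharge | proportion and incidence | score 0 to 10, no condition |

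Let p be the proportion with any nausea and s the share of those whose nausea required medication. The recorded proportion is s × p, which cannot exceed p. Since s is not collected, p cannot be recovered.

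**Possible size of the shortfall.** The background gives up to one third or more of patients with nausea or vomiting after surgery. Take p = 33% and, as an assumption with no source in the documents, s between one third and one half. The recorded rate is then 0.33 × 1/3 = 11% to 0.33 × 1/2 = 16.5%.

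**The plan's own sample size.** Inputs: "For a 2-sided test, with an alpha of 0.05 and a power of 90" percent, and "estimated effect size of 10% (p1= 80% and p2= 90" percent. With pooled variance and no continuity correction,

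n = [1.96 × √(2 × 0.85 × 0.15) + 1.2816 × √(0.80 × 0.20 + 0.90 × 0.10)]² / 0.10² = (0.990 + 0.641)² / 0.01, which rounds up to 266.

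This matches "a sample size of 266 per group was calculated". At the recruitment target of 275 per group the power for the primary outcome is 90.9%. The present point does not touch these figures.

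**Power for post-discharge nausea.** The plan gives none, so the rates below are assumptions: 275 per arm with everyone answering the call, any nausea 33% vs 23% (relative risk 0.23 / 0.33 = 0.70), and s = 0.5 in the higher-rate arm. For rates p1 and p2 with mean m and difference d,

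power = Φ[(d − 1.96 × SE0) / SE1], where SE0 = √(2m(1 − m)/275) and SE1 = √([p1(1 − p1) + p2(1 − p2)]/275).

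| What is counted | Rates | SE0 | SE1 | Φ argument | Power |
|---|---|---|---|---|---|
| Any nausea | 33% vs 23% | 0.0383 | 0.0381 | 0.656 | 74% |
| Medication-requiring, same relative risk | 16.5% vs 11.5% | 0.0296 | 0.0295 | −0.271 | 39% |
| Medication-requiring, relative risk 0.5 | 16.5% vs 8.25% | 0.0281 | 0.0279 | 0.986 | 84% |
| Medication-requiring, same 10-point difference | 16.5% vs 6.5% | 0.0272 | 0.0269 | 1.737 | 96% |

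The break-even is a relative risk of about 0.55 on medication-requiring nausea. Above that the threshold costs power, and below it the threshold gains power.

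**The case against.** The strongest defence is that a medication-requiring endpoint is a reasonable choice and fits the rest of the protocol. The primary outcome already treats mild nausea as success, DSU nurses record pain and nausea that call for treatment, and for planning services, symptoms that need medication (together with the ER and readmission item on the same call) are arguably the ones that count. This stands as a defence of the endpoint. It does not stand as a defence of the wording: where the plan wants a threshold elsewhere, as for itching or respiratory depression in Table 1, it states one, and objectives 4 and 5 and the incidence claim state none.

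A second objection is that the item asks whether medication was required, not whether it was taken. A patient who vomited repeatedly and took nothing might still answer yes. That is correct, so it cannot be said that every untreated patient is recorded as no, or that the answer simply reflects what was available at home. Under either reading, symptoms below the threshold are left out.

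A reader might also infer that the narrower items necessarily cost power on both objectives. The documents do not support that. The loss appears only if the relative effect is the same at both thresholds, and power rises if the effect is concentrated in the more severe symptoms. The 33% is moreover a combined figure for nausea or vomiting after surgery. The background also says that incidence could not be calculated from the post-discharge studies it reviews.

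**Conclusion.** The mismatch is real and follows from the text without any assumption. Carried out exactly as written, the plan estimates medication-requiring nausea and vomiting, a lower bound on the quantities named in objectives 4 and 5 and in the significance section. How far below depends on the share needing medication, which the documents do not give. If that share is one third to one half of an assumed 33%, the recorded rate is 11% to 16.5%.

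The effect on the between-arm comparison has no fixed direction. The range of 39% to 96%, against 74% for any nausea, rests on assumed rates, an assumed share of one half and full response to the call. No stated power figure is contradicted, because none is stated for these objectives. The point is confined to two secondary objectives and one stated deliverable, and it is worth correcting because the correction is cheap.

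**What to change.** Split each item in two, in both Outcomes at Post-operative Day 1 and Appendix 1:

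1. Did you have any nausea (any vomiting) after leaving hospital, in the first 24 hours?
2. If yes, was it severe enough to require medication?

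Use the first answer for objectives 4 and 5 and for the incidence estimate, and report the second as a severity measure. This keeps the present endpoint and adds the one that was promised. The cost is two short extra questions on a call already planned, with the matching case record form fields.

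If the items cannot be changed, restate objectives 4 and 5 and the incidence claim as nausea and vomiting requiring medication after discharge. That costs only a wording change, but the incidence of any nausea or vomiting is then no longer a result of the trial.

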It is being appreciated that, research and health care delivery have not focussed much on the post discharge symptoms after day surgeries. In this direction, two crucial aspects are to be considered. Compared to inpatients, ambulatory surgery patients have less efficient access to health services.⁽¹⁸⁾ It is wrong to assume that the burden of pain, nausea and other symptoms, after ambulatory surgery patients, is not substantial. A significant number of patients suffer from continuing pain even at 24 hours, or a week after surgery.⁽¹⁹⁾ Up to 1/3rd or more number of patients suffer from nausea or vomiting after surgery. Studies have shown that differences in anesthetic management, and choice of medications (even with non-analgesic medications such as propofol or sevoflurane) have made a difference in patient's perception of pain in ambulatory surgeries in the first 24 hrs, and beyond.⁽¹⁹⁾ A systematic review noted that only around 30%-42% of studies on ambulatory surgery patients, assessed for pain, nausea, and vomiting after discharge.⁽²⁰⁾ Due to significant heterogeneity, and study limitations, appropriate figures of observed incidence could not be calculated. Several of the included studies were also not well designed. Similarly, day surgery patients can also suffer from chronic postsurgical pain (CSPS), at 1 year or more after surgeries. It has been observed that up to 10%-50% patients, and 2%-11%

Most Effective Opioid Analgesia in Ambulatory Surgeries: a randomized control, investigator blinded, parallel group with superiority design study of Morphine versus Hydromorphone

[name], Principal Investigator SJHH

[name], Principal Investigator HHS

patients, suffer from moderate and severe level of CPSP.⁽²¹⁾ The definition of CPSP, in terms of the duration after surgery, has not been clearly identified. However, persistence beyond 2 months is normally considered as CPSP.⁽²²⁾ Specific to day surgeries, not many studies have assessed the incidence of CPSP and its predictive factors. A recent, large observational study, involving 908 patients, observed a CPSP (moderate to severe) rate of 15.3% after day surgeries.⁽²³⁾ They found that surgical specialty, preoperative pain, preoperative analgesic use, acute postoperative pain, surgical fear, lack of optimism and poor preoperative quality of life, as factors predictive of CPSP.

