4	Global Impression of Change	Likert scale 1-7

Most Effective Opioid Analgesia in Ambulatory Surgeries: a randomized control, investigator blinded, parallel group with superiority design study of Morphine versus Hydromorphone
[name], Principal Investigator SJHH
[name], Principal Investigator HHS

5	Analgesic Use: Did you have to use any pain medications for more than 1 month, to help with pain, which started with or after Surgery?	Yes or No
---	---	-----------

Statistical Analysis: The study will be analyzed using an intention to treat approach. The individual outcomes along with their respective analyses method have been listed within the table 1. Broadly the dichotomous outcomes will be reported as proportions and analyzed using a chi-square test to detect a significant difference ($p<0.05$). Precision will be reported using 95% CI. Continuous outcomes will be analyzed using an unpaired 2-tailed student t test for significance ($p<0.05$). Means and standard deviations shall be reported along with 95% CI. We also plan to perform logistic multivariable regression analysis to account for the influence of baseline covariates, which are listed in appendix 1. A sensitivity analysis will be performed to compare the effects of laparoscopic surgeries vs open surgeries.

Trial Management: This trial will be conducted at 3 hospital sites affiliated with McMaster University, Hamilton: St Joseph's Hospital, McMaster University Hospital and Juravinski Hospital.

Data Management and Quality Control: All study data including CRFs of each patient, shall be securely stored at the central office. A summary table indicating study timeline from enrollment to final follow-up (<http://www.spirit-statement.org/title/>) shall be included for each patient.⁽²⁷⁾ CRF's will be collected as paper forms. They shall be periodically cross-checked for completeness and entered into a suitable electronic master file. All reports of incorrect randomizations, protocol violations or incomplete data shall be noted.

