APPENDIX 1: Study Patient Case Record Form with Details to be Recorded

DEMOGRAPHICS AND PATIENT INFORMATION TO BE OBTAINED FROM PATIENT RECORDS

Study Number: Site: SJH MUMC JH

1	Patient's Hospital ID Number		
2	Age		
3	Gender	M	F
4	Height		
5	Weight		
6	Allergy to NSAIDS	Y	N
7	Allergy to LAs	Y	N

INFORMATION TO BE GAINED FROM THE PATIENT MEETING

1	APFEL Score (for PONV prediction)		Collected on 4 items- separately
2	HADS Score (Hospital Anxiety Depression Scale)		Collected on 14 items- separately
3	PCS (Pain Catastrophizing Scale)		Collected on 13 items - separately
4	Presence of Preoperative Pain in the Surgical Area	Y	N
5	If YES: is it Mild/ Moderate/ Severe		
6	Presence of Chronic Pain (>4 months) in Other Parts of the Body	Y	N

Most Effective Opioid Analgesia in Ambulatory Surgeries: a randomized control, investigator blinded, parallel group with superiority design study of Morphine versus Hydromorphone
 [name], Principal Investigator SJHH
 [name], Principal Investigator HHS

7	If YES: is it Mild/ Moderate/ Severe		
---	--------------------------------------	--	--

SURGICAL DETAILS TO BE OBTAINED FROM THE SURGICAL RECORDS

1	Date of Surgery		
2	Diagnosis (Intraoperative)		
3	Actual Surgical Procedure		
4	Laparoscopic or Open	L O	
5	Surgeon		Initials
6	Start Time of Surgery		
7	End Time of Surgery		
8	Duration of Surgery		
9	Total Local Anesthetic Infiltration (mls)		

ANESTHESIA DETAILS TO BE OBTAINED FROM THE ANESTHETIC RECORD

1	Anesthesiologist		Initials
2	Dexamethasone 4mg or 8mg	Y N	
3	Midazolam	1 mg 2 mg	
4	Propofol (total dose used)		
5	Remifentanyl (total dose used)		
6	Fentanyl (total dose used)		
7	Sufentanil (total dose used)		

Most Effective Opioid Analgesia in Ambulatory Surgeries: a randomized control, investigator blinded, parallel group with superiority design study of Morphine versus Hydromorphone
 [name], Principal Investigator SJHH
 [name], Principal Investigator HHS

8	Any continuous infusion used	Propofol  Remifentanyl 	
9	Ondansetron Prophylaxis Dose		Given prior to extubation
10	Was there a delay in transferring patient to the PACU (applicable when the PACU is on hold-and protocol needs to be initiated by the OR anesthesiologist)	Y N	

APFEL SCORE: for Prediction of Post-Operative Nausea Vomiting

RISK FACTOR	SCORE (each gets 0 or 1)
Postoperative Opioids	
Non-smoker	
Female Gender	
History of PONV or Motion Sickness	
Total Score	

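### If the post-discharge pain scores are analysed as scores, the planned t test leaves the preoperative pain grade and the stratification factors unused, at a small cost in precision

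*Combined protocol and SAP*

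**What the plan says.** - **General rule.** Statistical Analysis states: "Continuous outcomes will be analyzed using an unpaired 2-tailed student t test for significance". Dichotomous outcomes get a chi-square test. The word that introduces these rules marks them as a broad outline.
- **Adjusted model.** The same section adds: "We also plan to perform logistic multivariable regression analysis to account for the influence of baseline covariates". The covariates are those of Appendix 1. The outcomes that this model covers are not named. No linear model or ANCOVA appears anywhere.
- **Baseline data.** Appendix 1 records "Presence of Preoperative Pain in the Surgical Area" as yes/no, followed by a mild/moderate/severe grade if yes. There is no 0-10 baseline pain score and no baseline interference score.
- **Stated prognostic role.** Patients Symptoms after Discharge reports one observational study of chronic postsurgical pain (CPSP) after day surgery: "They found that surgical specialty, preoperative pain, preoperative analgesic use, acute postoperative pain" and other factors predicted it.
- **What is collected later.** The next-day telephone call asks "What was your average pain score over the last 24 hrs, in 0-10 NAS scale". The 3-month package holds seven interference items, each 0-10, with no summary score defined.
- **What the objectives say.** Specific Objectives words 24-hour pain as a proportion and the 3-month outcome as the incidence of CPSP. Interference is not a listed objective.
- **Table 1.** It covers in-hospital outcomes only, so neither the 24-hour score nor the interference items has an analysis row.
- **Stratification.** Methods names site and laparoscopic/open surgery. Allocation and Randomization names centre only. Both factors are on the case record form.

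**The concern.** The plan intends to use its baseline covariates, but the one model form it chose cannot be fitted to a 0-10 score without cutting the score in two. For any post-discharge pain outcome kept as a score, the general rule leads to a comparison with no covariates. Variation between patients that is explained by pre-existing pain, by site or by surgical approach then stays in the error term and widens the confidence interval. A chance imbalance in a known prognostic factor would also be left in the point estimate, with no planned analysis of the score to set beside it.

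This has some bearing on what the trial promises. Study Significance says the trial will address the severity as well as the incidence of persistent pain at 3 months, and severity is carried by scores. The 3-month data come by mail, and the plan expects minimal attrition only for the primary outcome. Precision may therefore be scarcer at 3 months than 275 per arm suggests.

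**Working it through.** **Step 1. The plan's own figure.** Inputs from Sample Size Calculation: 80% against 90%, two-sided alpha 0.05, power 90%. With pooled variance under the null and no continuity correction:

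n = [1.960 × √(2 × 0.85 × 0.15) + 1.282 × √(0.8 × 0.2 + 0.9 × 0.1)]² / 0.10² = [0.990 + 0.641]² / 0.01 ≈ 266 per group.

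This matches the plan: "a sample size of 266 per group was calculated". Power is 90.0% at 266 and 90.9% at the recruitment target of 275. The figure concerns the binary primary outcome, and nothing below changes it.

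**Step 2. A reference effect for a continuous score.** The plan gives no SD or effect for these scores, so I take the difference that an unadjusted comparison at 275 per arm detects with 80% power (normal approximation):

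d = (1.960 + 0.842) × √(2/275) = 0.239 SD.

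**Step 3. Effect of adjustment.** With correlation r between the baseline pain category and the outcome, the residual variance is (1 − r²) times the unadjusted variance. Then power = Φ(0.239 / √[(2/275)(1 − r²)] − 1.960), and the interval narrows by 1 − √(1 − r²). The value of r is an assumption, because the documents do not give it.

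| r | Variance cut | CI narrower | Equivalent extra patients per arm, 275/(1 − r²) − 275 | Power |
|---|---|---|---|---|
| 0 | 0% | 0% | 0 | 80.0% |
| 0.1 | 1% | 0.5% | 3 | 80.4% |
| 0.2 | 4% | 2.0% | 11 | 81.6% |
| 0.3 | 9% | 4.6% | 27 | 83.6% |

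**Step 4. Why the range stops at 0.3.** The baseline is a four-level category (none/mild/moderate/severe). Under three assumed category splits it keeps about 64% to 84% of the r² of an underlying continuous score. An underlying r of 0.3 then gives a variance cut of about 6% to 8% instead of 9%, and power of about 82% to 83%.

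A rough binary check points the same way. Take the 15.3% rate of moderate-to-severe CPSP cited in the background, and assume that 30% to 70% of patients have preoperative pain. An odds ratio of 2 then corresponds to a phi correlation of about 0.10 to 0.12, an odds ratio of 3 to about 0.15 to 0.20, and an odds ratio of 5 to about 0.19 to 0.29.

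**Step 5. Fewer responders.** With an assumed 25% loss (206 per arm) and, for illustration only, the standardised effect of 0.266 from the background meta-analysis, unadjusted power is 77.0%. Adjusted power is 77.4%, 78.7% and 80.8% at r = 0.1, 0.2 and 0.3.

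Steps 3 and 5 count preoperative pain alone. The documents give nothing from which to size any further gain from site and laparoscopic/open.

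**The case against.** The strongest reply is that the plan never assigns a t test to these outcomes by name. They have no row in Table 1, the t test reaches them only through a broad rule, and the stated objectives for 24-hour pain and CPSP are binary. Analysed as worded, both would get a chi-square test, and the logistic model with the Appendix 1 covariates could adjust them for preoperative pain. This stands, and it is why the point is conditional on analysing scores as scores. It does not remove the point. A 0-10 score is what is collected at 24 hours, no cut-off is given to turn it into a proportion, and the interference items are scores too.

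Three stronger readings are tempting, and the documents do not support them.

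- *That preoperative pain is the baseline value of these outcomes, so that a correlation near 0.5 and a large saving in patients can be assumed.* The baseline is a coarse grade on a different scale, no baseline interference is taken, and the 3-month persistent-pain question is limited to pain that began with or after surgery. The background supports preoperative pain as a predictor of CPSP only. Its value for 24-hour pain is an assumption.
- *That the t test is biased or invalid.* Randomisation makes it unbiased, and its standard error already allows for chance imbalance.
- *That the yes/no persistent-pain outcome is also left unadjusted.* The logistic model may already cover it; the plan does not say.

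A reader might also point to the planned sensitivity analysis of laparoscopic against open surgery. It names no outcome or model, and it is described as a comparison of the two approaches, not as adjustment of the treatment effect.

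**Conclusion.** The point holds as a small and nearly free improvement. If the 24-hour pain score and the interference scores are analysed as continuous, the planned analysis ignores a collected covariate and the stratification factors. The likely cost is modest: for an effect with 80% unadjusted power at 275 per arm, power is lower by about 0.4 to 3.6 points, and intervals are wider than they need be by an amount that adjustment would cut by 0.5% to 4.6%. That range assumes correlations of 0.1 to 0.3, which the documents neither give nor rule out; anything larger lacks support for this baseline measure. The direction is secure but the size is not known. The outcomes concerned are secondary or unlisted, and the trial is powered for none of them. The primary analysis, the 266 per group and the validity of the t test are unaffected.

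**What to change.** In Statistical Analysis, before unblinding:

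1. State whether 24-hour pain is analysed as the collected 0-10 score or as a proportion, and bring Specific Objectives into line. If it is a proportion, give the cut-off.
2. Define one summary score for the seven interference items.
3. For these continuous post-discharge scores, replace the t test by a linear model with treatment, site, laparoscopic/open and preoperative pain category (none/mild/moderate/severe). Report the adjusted mean difference with its 95% CI, and keep the t test as supportive.

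The cost is SAP wording, a few degrees of freedom out of about 550 patients, and a simple stated rule for missing baseline grades. No new data are needed, because the covariates are already on the case record form. If the correlation proves weak, the extra terms cost almost nothing at this sample size.
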